The long-term goal of the ENLACE is to reduce obesity and obesity-related morbidity and mortality by increasing the number of Latinas who meet national PA guidelines for adults9. We hypothesize that Latinas at the PA intervention sites will significantly increase their MVPA levels as a result of addressing their specific individual and environmental barriers and enhancing their social support and collective efficacy, compared to Latinas at the attention-control sites.

Primary aim: Test the effect of a 16-week, promotora-led PA intervention on minutes per week of MVPA (primary outcome) among Latinas in South Texas, compared to an attention-control group.

Secondary aims: a) Test the effect of the 16-week promotora-led PA intervention on physical fitness and weight maintenance (secondary outcomes); b) assess the maintenance of primary and secondary outcomes 6 months after the end of the intervention; c) examine the role of self-efficacy for PA, social support, decisional balance, and collective efficacy as mediators of changes in MVPA; and d) evaluate the impact of Latinas' social and community environment context on their success (or failure) in increasing MVPA and maintaining the behavior change.

Eight community resource centers (CRCs) in four Lower Rio Grande Valley (LRGV) counties—Starr, Hidalgo, Willacy and Cameron—will be randomly assigned to either the ENLACE PA Intervention (4 CRCs) or the attention-control condition (4 CRCs). We will recruit 864 Latinas ages 18 - 64 who do not meet national PA guidelines from colonias (unincorporated settlements where many people live in impoverished conditions and lack basic services) in the service area of the eight CRCs. Participants from CRCs randomized to the ENLACE PA Intervention (N = 432; 108 women per CRC) will receive the 16-weekly promotora-led group sessions, followed by 24 weeks of a maintenance intervention (monthly promotora-delivered newsletter and bi-monthly telephone counseling). The goal for the 16 weeks will be for women to engage in 30 minutes per day of MVPA on 5 or more days per week. The attention-control group (N = 432; 108 women per CRC) will receive 8 promotora-led group sessions twice a month on home safety/first aid and monthly generic health education materials during the maintenance intervention period. Standardized measurement of primary and secondary outcomes will occur at baseline, immediate (16 weeks) and delayed (40 weeks) post-intervention.

2. Background.

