(9)	
Describe measures taken to minimize the possibility of coercion or undue influence during consent.
 
Participants will be informed that their participation is voluntary in nature, that they may cease participation at any time and that their refusal to participate in the research study will not affect their relationship with the CRC or UTHSCSA.

(10)	
Will subjects from this population be assigned to different research groups? (e.g., treatment and control group)
 
 Yes  No
 
If yes, list the groups by inserting a short descriptive title for each group. E.g., experimental group A, B, etc., control group, etc. - these labels are needed for the Risk: Benefit Analysis section
 
 1. Intervention Group 2. Control Group

FORM C

IRB #	HSC20110460H
--------------	---------------------

4.c. For each specific population identified in **4b**, provide the following information in the table provided below.
*(For studies with **more than one** population, copy all of table 4.c. and paste to insert additional tables.)*

Population # 3		Population Descriptive Label: In-Depth Interview Participants
(1)	Identify the criteria for inclusion:	
	Participants will be a sub-set of the participants (women 18 thru 64 years old who self-identify as being of Hispanic) who participated in the PA intervention. All participants in the PA intervention that complete the 16 week immediate post intervention assessment will be in the population to be sampled for the qualitative interviews. After each cohort completes the 16 week assessment, 4 participants per CRC, stratified by success or failure (based on level of improvement in MVPA), will be randomly selected to take part in a two-part series of individual, in-depth interviews (N=64). Participants will be classified as successful if they show a minimum increase of 15 minutes/day MVPA (objectively measured).	
(2)	Identify the criteria for exclusion:	
	Participants who participated in the PA intervention but did not complete the 16-week immediate post intervention assessment or did not show a minimum increase of 15 minutes/day MVPA (objectively measured) will not be eligible to participate in the in-depth interviews.	
(3)	Recruitment Process – identifying potential subjects	

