Perceived Stress Scale (PSS-10) examines the degree to which specific situations are deemed as stressful in the past week. The PSS is well validated and has been used in many studies examining the association between stress and health⁹⁵.

Perceptions of Environmental Supports. The 10 items were adapted from the International Physical Activity Prevalence Study (IPS) Self-Administered Environmental Module to assess environmental supports and capture participants' sense of community opportunities for PA.

Food Frequency Questionnaire (FFQ) is approximately a 110 food item questionnaire designed to estimate usual and customary intake of a wide array of nutrients and food groups that is to be conducted by interviewer-administration.

Demographic Variables:

Demographic data (collected at baseline only) will be used to describe the study participants and facilitate statistical analyses where potential confounding by these variables should be controlled. Information will include age, current marital status, educational attainment, acculturation, nativity, current employment status and occupation, household size, family income.

In-Depth Interviews:

Individual in-depth interviews will be conducted with a subset of participants in the PA intervention. The purpose of the interview is to explore participants' personal experiences of behavior change and identified barriers and enablers to success/failure, including intrapersonal, social and environmental influences (Aim 2d). These qualitative data will complement and explicate quantitative findings from the intervention (Aim 2c). All participants in the PA intervention that complete the 16 week immediate post intervention assessment will be in the population to be sampled for the qualitative interviews. After each cohort completes the 16 week assessment, 4 participants per CRC, stratified by success or failure (based on level of improvement in MVPA), will be randomly selected to take part in a two-part series of individual, in-depth interviews (N=64). Participants will be classified as successful if they show a minimum increase of 15 minutes/day MVPA (objectively measured). Each participant selected will be interviewed twice, immediately after the 16 week and 40 week assessments.

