Qualitative Data Analysis Plan. Audio recordings of interviews will be transcribed verbatim in the source language and returned to the PI in paper and electronic (Microsoft Word) formats. A data collection assistant will review the paper transcripts for quality control purposes to make sure that the paper and electronic transcripts are as accurate and reflective of the interview as possible. All identifying information will be removed from transcripts. The transcript files will be imported into AtlasTi software for qualitative data management and analysis. All data in paper format will be stored in locked cabinets in locked offices. [name] will lead the qualitative analysis of the interview data in the source language, using thematic analysis procedures and the constant comparison method^{97,106}. For presentation and dissemination, selected excerpts of the Spanish-language qualitative data will be translated into English.

Power and Sample Size: Power calculations were conducted to determine the minimum detectable effect size based on a desired power achievement =0.80 using Optimal Design¹⁰¹. Setting the standard effect size to 0.50 and an expected intraclass correlation of .01, we have calculated a minimum number of 83 subjects per site will be needed. Based on a 76% retention rate from the pilot study, we will sample an additional 25 subjects to maintain statistical power throughout study duration for a total of 108 per site and an overall total of 864 subjects.

In-Depth Interviews: With a resulting sample of 96 interviews, we anticipate meeting the requisites of saturation and sufficiency⁹⁶. Saturation refers to the point in the study at which analysis of the interview data results in no new properties or dimensions⁹⁷. The greater the amount of pertinent (on-topic) data obtained from participants, the smaller number of participants required for saturation; thus, well-devised and conducted interviews with skilled probing reduces the need for large sample sizes in order to fully assess the phenomena under study⁹⁸. Sufficiency is the extent to which the participant sample encompasses the range of variability in the participant characteristics, especially those of known relevance to the topic⁹⁹. Due to the relative homogeneity of our participants, a sample of 96 interviews is expected to be sufficient.

6.b. List of the study intervention(s) being tested or evaluated under this protocol

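### The interview exclusion criterion bars the women whom the sampling rule classes as failures, and the stated N=64 does not follow from the design, which gives 48 women and 96 interviews

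*Protocol*

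**What the plan says.** Secondary aim (d) in Section 1 concerns the influence of Latinas' "social and community environment context on their success (or failure) in increasing MVPA" and in maintaining that change. The In-Depth Interviews paragraph under Measurement and Evaluation (Section 6.a) says the interviews serve this aim and are meant to "explore participants' personal experiences of behavior change and identified barriers and enablers to success/failure".

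The sampling rule appears in Section 4.c, Population 3, item (1) (inclusion), again in item (3) (identifying subjects), and again in Section 6.a:

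- Frame: "All participants in the PA intervention that complete the 16 week immediate post intervention assessment will be in the population to be sampled".
- Selection, after each cohort: "4 participants per CRC, stratified by success or failure (based on level of improvement in MVPA), will be randomly selected".
- Classification: "Participants will be classified as successful if they show a minimum increase of 15 minutes/day MVPA (objectively measured").

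Item (2) of the same table (exclusion) shuts out non-completers and, in addition, women who "did not show a minimum increase of 15 minutes/day MVPA (objectively measured) will not be eligible to participate in the in-depth interviews". Item (4) then has promotoras approach women drawn at random from those eligible at their center.

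On numbers, all three statements of the sampling rule give 64; in Section 6.a, for example, the women chosen "will be randomly selected to take part in a two-part series of individual, in-depth interviews (N=64"). The Study Design diagram in Section 3 shows 48 at 16 weeks and 48 at 40 weeks. The In-Depth Interviews paragraph under Power and Sample Size reads: "With a resulting sample of 96 interviews, we anticipate meeting the requisites of saturation and sufficiency".

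**The concern.** An exclusion criterion and a sampling rule for the same sub-study use one cut-off in opposite ways. The sampling rule uses 15 minutes/day to divide completers into two strata; the exclusion criterion uses it to remove one of them. Staff who interview a woman below the cut-off enroll someone the form calls ineligible. Staff who leave her out break the stratified draw.

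What is at stake is the composition of the interview sample. Barriers reported only by women who improved cannot be set against those of women who did not. The protocol also justifies the sample by its coverage of variability in characteristics relevant to the topic (the sufficiency argument under Power and Sample Size), and a sample confined to one side of the outcome weakens that argument. Analysis cannot repair this later, because each cohort's 16-week interview takes place once.

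The conflict over N is a separate and smaller matter: a reader cannot tell whether 48 or 64 women are to be interviewed.

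**Working it through.** **Eligibility against strata.** Let D be a woman's change in accelerometer MVPA from baseline to 16 weeks, in minutes/day.

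| Rule | Place in the protocol | Condition |
|---|---|---|
| Frame | Section 4.c Pop. 3 (1), (3); Section 6.a | PA arm, completed 16 weeks |
| Success stratum | same places | D >= 15 |
| Failure stratum | same places, by complement | D < 15 |
| Excluded | Section 4.c Pop. 3 (2) | not completed, or D < 15 |

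Eligible women are completers with D >= 15. Failure stratum and eligible: D < 15 and D >= 15, which no woman satisfies. The protocol does not define failure separately. A narrower definition, such as no gain or a decline, would still lie below 15 and would still be excluded. Because item (4) draws from eligible women, the exclusion operates before selection.

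For scale, 15 minutes/day is 15 x 7 = 105 minutes/week, against a behavioral goal of 30 x 5 = 150 minutes/week. Women with real but smaller gains are therefore excluded as well.

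**Number of women.** Inputs from Section 3: 4 intervention participants per center in each cohort, 4 intervention centers, 3 cohorts, 2 interviews each.

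- Women: 4 x 4 x 3 = 48. This reproduces the diagram.
- Interviews: 48 x 2 = 96. This reproduces the sample-size paragraph.
- Stated N=64, read as women: 64 x 2 = 128 interviews, not 96; and 64 / (4 x 3) = 5.33 women per center and cohort, not a whole number and not 4.
- Stated N=64, read as interviews: 64 / 2 = 32 women, not 48.
- Excess over the design: 64 - 48 = 16 women; 16 / 48 = 33%.

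Combinations that do give 64:

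- 4 women x 4 centers x 4 cohorts
- 4 women x 8 centers x 2 cohorts
- 4 women x 4 centers x 2 cohorts x 2 interviews
- 4 women x 8 centers x 1 cohort x 2 interviews

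Each departs from the stated 3 cohorts, and those with 8 centers also depart from sampling in the intervention arm only.

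**The case against.** The best defense is that this is a drafting slip. Three statements of the sampling rule, the aim in Section 1 and the design overview in Section 3 all point to sampling both strata; half a sentence disagrees. That is a fair account of the likely intent, and it is why the consequence must be stated conditionally. It does not remove the conflict, because the half-sentence is the formal exclusion criterion on the IRB form and item (4) makes eligibility govern the draw.

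A reader might go further than the documents allow in three ways.

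- **That aim (d) cannot study failure at all.** The aim also covers maintenance, and each woman is interviewed again after the 40-week assessment, so failure to maintain can be studied among women who had improved at 16 weeks. Perceived environmental supports and collective efficacy are measured by questionnaire three times (Section 6.d), and perceptions over time enter the mixed models (Section 6.a). What goes missing is interview evidence on failure to increase MVPA by 16 weeks.
- **That half the interviews are lost.** The rule still selects 4 women per center and cohort, so all 96 interviews could take place, all with women who improved. The protocol also states no split between strata, so no count of displaced failures can be derived from it.
- **That choosing women by outcome is itself the fault.** The stratified design does this deliberately. The fault is restriction to one stratum.

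It also stands that randomization, the primary MVPA comparison and its sample size (83 per site, 864 in total) are untouched, and that the error in N is editorial, since the diagram and the sample-size paragraph already agree with each other.

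**Conclusion.** Both contradictions are real. Applied as written, the exclusion criterion empties the failure stratum at 16 weeks, whatever split between strata was intended. The interviews would then offer no contrast between women who did and did not increase MVPA by that time. This is conditional on the exclusion line being followed in preference to the sampling text. N=64 is 33% above the 48 women that the protocol's own design yields; 48 women and 96 interviews reproduce exactly.

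Severity is should-fix: the effect is confined to a qualitative sub-study serving one part of a secondary aim.

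**What to change.** In Section 4.c, Population 3, item (2), delete the second condition (the one requiring a gain of at least 15 minutes/day), leaving non-completion of the 16-week assessment as the only exclusion. Both strata can then be sampled as items (1) and (3) and Section 6.a describe.

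Replace N=64 with 48 women (96 interviews) in Section 4.c, Population 3, items (1) and (3), and in the In-Depth Interviews paragraph under Measurement and Evaluation in Section 6.a. The diagram and the sample-size paragraph need no change.

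The investigators should state how the 4 women per center and cohort are divided between the strata; the protocol gives no basis for a particular split.

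The cost is a wording amendment to the IRB form, with no interviews beyond the 96 already planned. It should be in place before the first cohort's 16-week selection.

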We propose a 5-year study to test the effectiveness of a culturally appropriate, theory-based intervention to increase MVPA among Latinas in the LRGV. This study is a continuation of our ENLACE pilot study. We will involve 8 CRCs affiliated with the Colonias Program in the study. The CRCs will be randomized to one of two conditions: (a) ENLACE PA intervention (n=4 CRCs), or (b) attention control (n=4 CRCs). By randomizing at the CRC-level the intervention can be implemented by the promotora to all study participants, thus reducing the risk of contamination that would be present with promotora- or participant-level randomization. This approach also allows us to implement an ecological intervention, where each CRC can implement and promote PA activities and display materials to support the intervention messages. A total of 864 Latinas ages 18-64 years will be recruited from within the service area for these 8 CRCs. The study will be conducted in 3 cohorts of 288 women (36 per CRC in each cohort). Participants will be assessed at baseline, 16 weeks (immediate post intervention), and 40 weeks (delayed post intervention). The primary outcome is minutes per week of MVPA. Secondary outcomes are physical fitness and weight maintenance. Consistent with our approach, we will establish a community advisory group and engage promotoras in conducting participatory community assessments. Finally, we will recruit sub-sample of 4 intervention participants from each CRC cohort to complete two in-depth interviews, immediately following the PA intervention (16 weeks) and after the maintenance intervention period (40 weeks), to evaluate the impact of Latinas’ social and community environment context on their success (or failure) in increasing MVPA and maintaining the behavior change.

Study Design

```

graph TD
    A[8 promotoras] --> B[8 groups of 8-10 women per group (n=68)]
    A --> C[Baseline Assessment N=864]
    C --> D[Randomize]
    D --> E[Physical Activity Intervention (n=432)]
    D --> F[Attention Control (n=432)]
    E --> G[16-week Assessment]
    G --> H[In-Depth Interviews (n=48)]
    H --> I[40-week Assessment]
    I --> J[In-Depth Interviews (n=48)]
    F --> K[16-week Assessment]
    K --> L[40-week Assessment]
    
```

FORM C

IRB #	HSC20110460H
--------------	---------------------

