(3)	
Recruitment Process – identifying potential subjects Describe plans about how the population will be identified for the purpose of recruiting. (e.g., database search, personal contacts, referrals, patients under the care of the research team, etc.)
 
With support from the Colonias Program, we will involve 8 CRCs in the trial. Promotoras will recruit through existing social networks. Recruitment will take place at neighborhood and community settings located within the CRC's designated service area.
 
Who will access PHI to identify potential participants? Select one Note: Not applicable because recruitment will occur through community outreach. No database or PHI will be accessed to identify eligible participants.
 
 
 	Only those with existing legitimate access to PHI will use it to identify potential subjects	
 
 	There is a need to allow those without existing legitimate access to PHI to use it to identify potential subjects (submit Form J, HIPAA Waiver)	
 
		Only those with existing legitimate access to PHI will use it to identify potential subjects		There is a need to allow those without existing legitimate access to PHI to use it to identify potential subjects (submit Form J , HIPAA Waiver)
	Only those with existing legitimate access to PHI will use it to identify potential subjects				
	There is a need to allow those without existing legitimate access to PHI to use it to identify potential subjects (submit Form J , HIPAA Waiver)				

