	C (2) In order to ensure that individuals are appropriately informed about the study when English is their second-language, describe a plan for evaluating the level of English comprehension, and the threshold for providing a translation, or explain why an evaluation would not be necessary. 
Participants will choose their language of preference.

6. Research Plan / Description of the Research Methods:	
6.a. Provide a comprehensive narrative describing the research methods . Provide the order in which tests/procedures will be performed , the setting for these events and a description of the methods used to protect privacy during the study. Provide the plan for data analysis (include as applicable the sample size calculation)	

FORM C

IRB #	HSC20110460H
-------	--------------

Randomization. After baseline data collection, random assignment to experimental condition will use the following procedure: the PI will designate 8 slips of paper as intervention or control (4 intervention, 4 control) and place them into individual sealed envelopes. The sealed envelopes will be shuffled and assigned a number 1 through 8 (written on the outside of the envelope) and given to the Measurement Coordinator in a larger envelope. As each center completes baseline assessments for the first cohort, the Measurement Coordinator will draw an envelope and open it, and will record the CRC name and group assignment into a tracking database. Once randomized, the CRC will remain in the same condition for all 3 cohorts.

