D.4.2.4. Environmental Change. Social ecological models^{33, 34, 78} emphasize that the environment is an important influence on health behavior. We will work with *promotoras* at the four ENLACE PA intervention CRCs to create a site atmosphere that promotes PA. Examples might include educational posters, promotional activities to increase awareness and appeal of existing resources, notices of related community events, and a display board highlighting the ENLACE Program and participants who have been successful in the program. *Promotoras* will also increase the number of PA program offerings at the CRC by identifying and training volunteer walk leaders and using an exercise DVD library to offer regularly scheduled group exercise classes.

D.4.2.5. Attention Control Intervention. Attention control participants will receive a research-tested first aid and home safety program developed for Hispanic migrant adolescents and their families⁷⁹. We selected the home safety/first aid as the attention control condition because changes in these behaviors should have no impact on PA, the curriculum is available in Spanish, and has been shown to improve first aid knowledge and emergency response skills. In addition, the *Colonias* Program staff indicated it was relevant topic for families in the *colonias*. The program includes 8 sessions that last 1.5-2 hours. These sessions will be offered twice per month to extend them over a 16 week period. The session content ranges from identifying household safety hazards to disaster preparedness. During the 24 week maintenance phase, *promotoras* will contact participants by phone each month and conduct monthly home visits to distribute health education materials on first aid and home safety from CDC, state health department and other reliable health organizations (e.g., Red Cross). Attention control participants will not receive telephone counseling calls.

Measurement and Evaluation

Standardized data collection protocols will be carried out for all participants at baseline, 16-, and 40-weeks.

Primary Outcome Measures:

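### Two-thirds of the women (cohorts 2 and 3) are recruited, screened and baseline-assessed after their CRC's arm is known, so assignment after baseline holds only for cohort 1 and a route to selection bias is open

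*Protocol*

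**What the plan says.** The Randomization paragraph in section 6.a of the protocol opens without limiting itself to a cohort: "After baseline data collection, random assignment to experimental condition will use the following procedure". A few sentences later it gives the actual trigger: "As each center completes baseline assessments for the first cohort, the Measurement Coordinator will draw an envelope and open it". It then adds: "Once randomized, the CRC will remain in the same condition for all 3 cohorts".

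Section 3 (D.2.1) sets the cohort structure, "The study will be conducted in 3 cohorts of 288 women (36 per CRC in each cohort", and the total, "A total of 864 Latinas ages 18-64 years will be recruited from within the service area for these 8 CRCs". The design figure in that section, which survives as flowchart text, has the node "C[Baseline Assessment N=864" ahead of the randomisation step.

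On who does what:

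- **Recruitment.** Section 4.c, Population 2, item (3): "Promotoras will recruit through existing social networks".
- **Screening.** Item (4) has the promotora telephone each interested woman and run the eligibility screen. Item (2) rests the activity exclusion on self-reported answers to six questions.
- **Delivery.** Promotoras lead the group sessions in both arms (sections 1, D.2.4.2 and D.4.2.5).
- **Consent and measurement.** Items (7) and (8) have research staff take consent after screening and before baseline. Section 6.a ties completion of baseline to a Measurement Coordinator. No passage has promotoras doing baseline testing.
- **Site environment.** At intervention centres, D.4.2.4 says promotoras "will also increase the number of PA program offerings at the CRC", and lists posters and a display board as possible examples.

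**The concern.** In a cluster-randomised trial, randomisation protects the comparison of individuals only if they are identified before the cluster's arm is known, or by someone who does not know it. Here that protection covers one cohort of three. From cohort 2 on, the promotora has already been running either an exercise programme or a first-aid programme. She chooses whom to invite from her own network, and she asks the activity questions that decide eligibility. Women must also be willing to attend the sessions, and by then it can be known locally which sessions their centre offers.

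If women keen to exercise come forward, or are invited, more often at intervention centres, the arms differ in who enrolled as well as in what they received. Intention-to-treat analysis does not repair this, because the difference arises before enrolment. The protocol justifies randomising centres by the risk of contamination, which is a separate issue.

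**Working it through.** **1. Reproduce the total.** Inputs: 36 women per CRC per cohort, 8 CRCs, 3 cohorts (section 3, D.2.1).

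- 36 × 8 = 288 per cohort.
- 288 × 3 = 864, which matches the stated total.

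**2. Share enrolled after allocation.** Each envelope is opened at the end of that centre's first-cohort baseline, and the arm is then fixed. The protocol does not say outright that the cohorts run in sequence, but this follows from that trigger.

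- Before allocation: 288 / 864 = 33.3%.
- After allocation: 2 × 288 = 576, and 576 / 864 = 66.7%. That is 288 of 432 per arm and 72 of 108 per CRC.

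**3. Set the statements side by side.** The opening sentence on randomisation and the design figure both put baseline before assignment, and the figure does so for all 864. The trigger and the fixed-arm rule make that order possible only for the first 288.

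**4. Check the safeguards.** Eligibility criteria are the same in both arms, the screening call is scripted, and research staff take consent. None of these hides the arm from the recruiter or the candidate, and none controls whom the promotora approaches. The protocol describes no recruiter independent of delivery, no list of candidates drawn up before allocation, and no masking of baseline assessors.

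**5. Possible size.** The documents give no figure for selection, so this step is an illustration. Let b be the between-arm difference in the baseline-adjusted outcome that arm-aware recruitment creates in cohorts 2 and 3, with none in cohort 1. With cohorts weighted by size, the shift in the pooled contrast is (576 / 864) × b.

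| Assumed b (SD) | Shift in pooled contrast (SD) | Share of the stated 0.50 |
|---|---|---|
| 0.1 | 0.667 × 0.1 = 0.067 | 13% |
| 0.3 | 0.667 × 0.3 = 0.200 | 40% |

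**6. What cohort 1 alone could show.** Inputs: 36 per CRC, 76% retention and ICC .01 (Power and Sample Size), giving 36 × 0.76 = 27.4, taken as 27 per CRC. I assume a two-sided 5% t test on 8 − 2 = 6 df. The standard error in SD units is √{4[ρ + (1 − ρ)/n] / 8} = √{4[0.01 + 0.99/27] / 8} = 0.153.

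- Effect 0.50: noncentrality 0.50 / 0.153 = 3.27, power about .78.
- Effect 0.35: noncentrality 0.35 / 0.153 = 2.29, power about .49.

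The second effect is roughly what 83 per CRC can detect with 80% power on the same formula (power .79 at 0.35).

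**The case against.** The sequence is not hidden: the paragraph that opens loosely states the first-cohort trigger and the fixed arm a few sentences later, and the figure is a simple schematic. That makes the contradiction one of wording. It does not change when the 576 women enter.

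The size is not anchored in the documents. The 0.1 to 0.3 SD is purely assumed. The analysis section models repeated measures and looks at change from baseline, so a difference in activity level alone would be partly removed. Only a difference that persists after baseline adjustment biases the effect. This stands, and b is defined accordingly.

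A reader might infer three stronger things that the documents do not support:

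- **Promotoras carry out the baseline tests.** The text points to research staff and a Measurement Coordinator. The promotoras' role before enrolment is recruitment and screening.
- **Cohort 2 and 3 baselines are already contaminated by exercise activities at the centre.** D.4.2.4 gives no schedule, and posters are only examples of what might be done. Such exposure is an inference. If it raised baseline activity it would shrink measured change and could bias towards the null, opposite to the effect of recruiting motivated women.
- **Cohort 1 is a clean and decisive check.** Its power is modest at 0.35 SD. With four slips for each arm drawn in turn, the last centre's arm is determined before its envelope is opened. Cohort 1 may also differ from later cohorts in promotora experience and site environment, so a difference between cohorts would not isolate selection.

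Finally, a cohort term or sensitivity analysis may sit in a statistical analysis plan that is not shown. Its absence from the protocol is not part of the finding.

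**Conclusion.** The point holds, and the protocol should be changed. By its own text, 576 of 864 women (67%) are recruited and screened by promotoras who already know and deliver their centre's arm, and have their baseline after allocation. The statement that assignment follows baseline is true only for the 288 women of cohort 1. The count is exact, given that the cohorts run in sequence.

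The resulting bias is possible but not demonstrated, and neither its size nor its net direction can be fixed from the documents. The illustrative shift of 0.07 to 0.20 SD rests wholly on the assumed 0.1 to 0.3 SD difference after baseline adjustment. The design remains usable; the fault is an unguarded and misdescribed route to selection bias.

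**What to change.** 1. **Correct the text and figure.** In the Randomization paragraph and the design figure, say that assignment follows baseline in cohort 1 and precedes recruitment and baseline in cohorts 2 and 3.
2. **Protect recruitment in cohorts 2 and 3.** Use the same arm-neutral invitation and screening script at all eight CRCs. Tell women which programme their centre offers only after the baseline visit, as far as the consent process allows. Have the research staff who already take consent confirm the activity eligibility items.
3. **Make the cohorts visible in the analysis.** Include cohort in the model, and pre-specify a baseline comparison by arm within cohort and a cohort 1 estimate as a supportive sensitivity analysis. Present that estimate as a check (power about .78 at 0.50 SD, about .49 at 0.35 SD), not as decisive. These items can go in the statistical analysis plan.

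The cost is protocol and script wording, a short staff check at consent, and a little extra analysis. The limit is that masking at recruitment will be imperfect, because a centre's activities can be seen locally, and a neutral script does not fully remove the promotora's choice of whom to invite.
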